1.2.1.1.2 Safety pharmacology and toxicology

BGJ398 showed no evidence of *in vitro* genotoxicity in Ames and chromosome aberration tests and no evidence of phototoxicity in a 3T3 photo-cytotoxicity test. *In vitro* safety pharmacology assessment of BGJ398 revealed a decrease in human *Ether-à-go-go*-related gene (hERG) channel activity with an IC_{50} of $2.0\mu M$ (1121ng/ml).

In vivo safety pharmacology studies in rats and dogs did not reveal any effects on central nervous or respiratory systems and on hemodynamic or electrocardiographic parameters, respectively.

In repeated dose (oral gavage; up to 4-weeks) toxicity studies, BGJ398 did lead to increases in serum FGF23 and serum phosphorous associated with partially reversible ectopic mineralization (kidney, lung, vascular and digestive systems) along with largely reversible changes in renal function parameters and bone growth plate thickening / retention of the primary spongiosa in rats ($\geq 10\text{ mg/kg/day}$) and dogs ($\geq 10\text{ mg/kg/day}$). These effects were deemed to be on-target effects mediated by pharmacological inhibition of FGFR.

In rats, corneal changes were found upon 4 weeks of BGJ398 treatment consisting of irreversible, slight corneal opacity in dose-dependent incidence, as assessed by *in vivo* ophthalmology, associated with reversible, diffuse epithelial keratopathy at the highest dose of 10 mg/kg . In the 4-week GLP oral toxicity study in rats, the severely toxic dose in 10% (STD_{10}) was 10 mg/kg/day which resulted in premature death in one (1/30) animal. Doses of 20 mg/kg/day in rats led to vasculopathy associated with moribundity after 6 administrations. In dogs, the highest non-severely toxic dose (HNSTD) was 10 mg/kg/day leading to minimal, fully reversible retention of the primary spongiosa and minimal increase in mineralization in lung and kidney without observed functional impairment.

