1.2.1.2 Clinical experience

1.2.1.2.1 Clinical safety

As of November 6, 2014, 226 patients have received BGJ398 on one of the eight clinical trials. In addition to this phase II trial, BGJ398 is being evaluated in three phase I trials, one other monotherapy phase II study, two healthy volunteer studies and an individual patient protocol

(protocol to patient trial) that provides BGJ398 treatment to patients with tumors with FGFR genetic alterations who are not covered by available trials or are unable to travel to study centers. The dose escalation portion of the first in human phase I study (CBGJ398X2101) has been completed and the MTD has been identified as 125 mg once daily (q.d.), administered continuously. BGJ398 was evaluated at 9 different dose levels, ranging from 5 mg per day to 150 mg per day. The adverse events suspected to be related to BGJ398 that occurred in more than 20% or more patients who received BGJ398 were hyperphosphatemia (71.3%), decreased appetite (26.6%), fatigue (25.5%), stomatitis (24.5%), and alopecia (21.3%). Twenty-seven percent of patients (26/94) experienced at least one grade 3 or 4 event. Overall, most adverse events reported have been mild to moderate in severity and unrelated to BGJ398. Please refer to Investigator Brochure for more information.

Four dose limiting toxicities (DLTs) were reported during the dose escalation portion and occurred at the 100 mg (n=1; grade 3 AST/ALT elevation), 125 mg (n=1; hyperphosphataemia for > 14 days), and 150 mg (n=2; grade 1 corneal toxicity and grade 3 AST/ALT elevation) dose levels.

Enrollment is continuing in the dose expansion phase of the study at the 125 mg dose level in three out of four arms. One arm, which enrolled patients with any solid tumor type with FGFR genetic pathway alterations on a continuous schedule, has been closed due to completing enrollment. Of the three open arms, one arm is enrolling patients with FGFR1-amplified squamous non-small cell lung cancer, with dosing on a continuous 28 day cycle. A second arm is enrolling patients with advanced solid malignancies with any FGFR alteration and a third arm is enrolling patients with advanced or metastatic urothelial cell carcinoma with FGFR mutation or gene fusion. Patients enrolled to these latter two arms receive BGJ398 at 125 mg q.d. on a 3 weeks on/1 week off drug schedule, repeated in 28 day cycles.

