6.2 Dose modifications

6.2.1 Dose modification and dose delay

For patients who do not tolerate the protocol-specified dosing schedule, dose adjustments are permitted in order to allow the patient to continue the study treatment. These changes must be recorded on the Dosage Administration Record CRF.

All dose modifications should be based on the worst preceding toxicity. The following guidelines need to be applied:

Each patient will be allowed up to 2 dose reductions. Patients must discontinue BGJ398 if toxicities persist following 2 dose reductions ([Table 6-2](#)) unless a continuation is allowed in discussion with Novartis.

Following resolution of toxicity to baseline or \leq grade 1, treatment is resumed at either the same or lower doses of study drugs as per the criteria in [Table 6-3](#). If treatment is resumed at the same doses of study drugs, and the same toxicity recurs with the same or worse severity regardless of duration, doses must be reduced to the next lower dose level ([Table 6-2](#)). If treatment is resumed at the lower doses of study drugs, and the same toxicity recurs with the same or worse severity, the patient must discontinue study treatment unless a continuation is allowed in discussion with Novartis.

If a patient requires a dose delay of > 14 consecutive days of BGJ398 from the intended day of the next scheduled dose, then the patient should be discontinued from the study treatment unless a continuation is allowed in discussion with Novartis.

Patients who discontinue the study for a study related adverse event or an abnormal laboratory value must be followed as described in [Table 6-3](#) and [Section 6.2.2](#).

In exceptional situations, study treatment may continue even if the patient experienced one of the treatment stopping rules. The decision to allow for continuation of treatment will be made on a case-by-case basis following discussion between Novartis and the Investigator.

Situations that may allow for continuation of treatment include but are not limited to the following.

- A dose delay of > 14 days has occurred, but the patient is clearly benefiting from study treatment (i.e., stable disease, partial response, or complete response) and it is the investigator's opinion that no safety concerns are present, after discussion with Novartis Medical Monitor, the patient may remain on the study treatment

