
Diarrhea
 
Grade 1
 
Grade 2
 
Grade 3
 
Grade 4
	
Maintain dose level of BGJ398, but initiate anti-diarrheal treatment
 
 ● Hold dose of BGJ398 until resolved to CTCAE Grade ≤ 1 ● Optimize anti-diarrheal treatment, maintain dose level of BGJ398. ● For reoccurrence of diarrhea CTCAE Grade 2, hold dose of BGJ398 until resolved to CTCAE Grade ≤ 1, ↓ BGJ398 by 1 dose level 
 ● Hold dose of BGJ398 until resolved to CTCAE Grade ≤ 1 ● Optimize anti-diarrheal treatment ● ↓ BGJ398 by 1 dose level ● For reoccurrence of diarrhea CTCAE Grade 3, despite optimal anti-diarrheal treatment, discontinue patient from study treatment. 
Discontinue patient from study treatment.
 
Note: Antidiarrheal medication is recommended at the first sign of abdominal cramping, loose stools or overt diarrhea

Vomiting
 
Grade 2 not controlled by optimal anti-emetic therapy
 
Grade 3 not controlled by optimal anti-emetic therapy or Grade 4
	
Hold BGJ398 doses until ≤ grade 1, ↓ 1 dose level
 
Discontinue patient from study

Worst Toxicity CTCAE using the current active CTCAE version	Recommended Dose Modifications any time during a cycle of therapy
Eye Disorders (confirmed by ophthalmologic examination)	

Retinal disorders
 
Grade 2 CSR and CSR-like events
 
Grade 3 CSR and CSR-like events and any other grade 3 eye disorders
 
≥ grade 1 retinal vein occlusion, grade 4 CSR and CSR-like events, and grade 4 other eye disorders
	
Hold BGJ398 until resolved to ≤ grade 1 and continue ophthalmologic evaluation
 
 ● If resolved in ≤ 14 days, ↓ BGJ398 by 1 dose level ● If resolved in > 14 days, discontinue BGJ398 
Hold BGJ398 until resolved to grade ≤ 1.
 
 ● If resolved in ≤ 14 days, ↓ BGJ398 by 1 dose level ● If resolved in > 14 days, discontinue BGJ398 
Discontinue BGJ398

Other ocular/visual toxicity
 
≥ grade 3
	
Hold BGJ398 until resolution to ≤ grade 1
 
If resolution in ≤ 14 days, ↓ 1 dose level, otherwise discontinue BGJ398

General disorders	

Fatigue
 
Grade 3
	
Hold dose of BGJ398 until resolved to CTCAE Grade ≤ 1
 
 ● If resolved in ≤ 7 days, maintain dose level of BGJ398. ● If resolved in > 7 days, discontinue patient from study treatment.
Other clinically significant AEs	

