
Grade 3
 
Grade 4
	
Hold dose of BGJ398 until resolved to CTCAE Grade ≤ 1, then ↓ 1 dose level of BGJ398.
 
Discontinue patient from study treatment.

All dose modifications should be based on the worst preceding toxicity. Once a dose has been reduced it will not be increased at a later time even if there is no toxicity. Patients who require more than two dose reductions of BGJ398 will be discontinued from study drug treatment.
 
If a patient requires a dose delay of > 14 days from the intended day of the next scheduled dose of BGJ398 then study treatment must be stopped.
	

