7.2.2.8 Ophthalmologic assessments

[figure not shown]
Ophthalmologic examinations will be performed as indicated in [Table 7-1](#) and includes: visual acuity testing, slit lamp examination of the anterior eye segment, intraocular pressure (IOP), and fundoscopy. Additional examination methods such as specular microscopy (that enables a magnified, direct view of the corneal endothelium), corneal pachymetry, and dilated fundoscopy will be performed as clinically indicated.

8 Safety monitoring and reporting

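### Table 6-3 gives two different instructions for a Grade 4 non-retinal eye event that resolves within 14 days, and nothing says which one governs

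*Protocol*

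**What the plan says.** Under its Eye Disorders heading, Table 6-3 (Protocol Section 6.2.1) has two labelled rows.

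- **Retinal disorders**, with three entries. The second covers "Grade 3 CSR and CSR-like events and any other grade 3 eye disorders". Its action is to hold until Grade 1 or less, go down one dose level if that takes no more than 14 days, and otherwise discontinue. The third covers "≥ grade 1 retinal vein occlusion, grade 4 CSR and CSR-like events, and grade 4 other eye disorders". Its action is to discontinue BGJ398, with no resolution window.
- **Other ocular/visual toxicity**, with one entry, triggered at Grade 3 or above. Its action is to hold until Grade 1 or less, and then: "If resolution in ≤ 14 days, ↓ 1 dose level, otherwise discontinue BGJ398".

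Section 6.2.1 and the closing note of the table both state: "All dose modifications should be based on the worst preceding toxicity". Section 6.2.1 also provides an exception: "In exceptional situations, study treatment may continue even if the patient experienced one of the treatment stopping rules". That decision is made case by case after discussion between the sponsor and the investigator.

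**The concern.** The third retinal entry reaches beyond the retina, because it names other eye disorders at Grade 4. The other-ocular row has no ceiling, so it also reaches Grade 4. A patient on 125 mg whose Grade 4 corneal event clears in ten days would be permanently off drug under one row. Under the other, the same patient could restart at 100 mg, the next level in Table 6-2.

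Front-of-eye toxicity is a recognised concern with this drug. Rats given it for four weeks showed "irreversible, slight corneal opacity in dose-dependent incidence" (Protocol Section 1.2.1.1.2). The two phase I dose-limiting toxicities at 150 mg were "grade 1 corneal toxicity and grade 3 AST/ALT elevation" (Section 1.2.1.2.1). The trial's own eye examination includes "slit lamp examination of the anterior eye segment" (Section 7.2.2.8). Section 12 allows no authorised deviations, so a site facing such an event cannot tell from the protocol whether a restart would comply.

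**Working it through.** No arithmetic applies. The check sets the two rows side by side for a non-retinal eye event and then looks for a rule that decides between them.

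**Step 1: final action by grade and time to reach Grade 1 or less**

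| Event | Entries under the retinal label | Other-ocular row | Same? |
|---|---|---|---|
| Grade 3, 14 days or less | Restart one level down | Restart one level down | Yes |
| Grade 3, more than 14 days | Discontinue | Discontinue | Yes |
| Grade 4, 14 days or less | Discontinue | Restart one level down | **No** |
| Grade 4, more than 14 days | Discontinue | Discontinue | Yes |

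One of the four cells conflicts. This counts rule combinations, not how often such events occur. In all four cells dosing stops as soon as the event is recognised.

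**Step 2: is there a tie-break?**

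- *Worst preceding toxicity* (Section 6.2.1 and table note). This picks the grade to act on. Here there is one event at one grade, and it meets both rows.
- *Resumption rule* (Section 6.2.1). It sends the reader back to Table 6-3 for the dose at restart.
- *Dose delay beyond 14 days* (Section 6.2.1 and table note). It does not reach an event that resolves inside 14 days.
- *Catch-all for other clinically significant adverse events*. Its Grade 4 line discontinues, which shows a leaning, but it does not say that it overrides a named row.
- *Drugs appearing on two lists* (Section 6.3). The stricter list wins, but the rule concerns concomitant medication only.
- *Case-by-case exception* (Section 6.2.1). It applies once a stopping rule has been met and does not say whether one has been.
- *The column heading calls the actions recommendations.* Section 6.2.1 introduces its guidelines as ones that have to be applied, so the heading does not make the choice optional.

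The SAP contains no dose-modification rules.

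**Step 3: what turns on the choice?** If the discontinue entry governs, a restart is possible only through the case-by-case discussion with the sponsor. If the other-ocular row governs, the investigator may restart one level down without it. That is the whole practical difference.

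**Step 4: evidence on frequency.** Section 1.2.1.2.1 reports four phase I dose-limiting toxicities: two Grade 3 AST/ALT elevations, one prolonged hyperphosphatemia and one Grade 1 corneal toxicity. None falls in the conflicting cell, and the documents give no rate for Grade 4 eye events.

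**The case against.** The best defence is the layout. Two labelled rows sit under one heading. If other eye disorders, placed under the retinal label, means other *retinal* disorders, the rows do not overlap and each has its own job. On the literal reading, the second row repeats the first at Grade 3 and contradicts it at Grade 4. This defence has some force as a guess at intent. It does not match the words: both the Grade 3 and the Grade 4 entries say eye disorders, which is the term the table uses for the whole block. Even if the sponsor meant the narrow reading, the text needs to say so.

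A second defence is that restart after a Grade 4 event is ordinary in this table. That is correct for Grade 4 neutropenia, hemoglobin and platelet events, all of which allow restart one level lower. A reader might infer that the other-ocular row is out of line with the rest of the table; those rows show that it is not. The defect is the contradiction, not leniency.

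A third defence is that the risk evidence is modest. This stands. The rat opacity was slight and the keratopathy seen with it was reversible. The corneal dose-limiting toxicity was Grade 1 and arose at 150 mg, above this trial's 125 mg starting dose. Exclusion criterion 23 also keeps out patients with current corneal or retinal disease.

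**Conclusion.** The point holds. As written, Table 6-3 gives contradictory stopping instructions for a Grade 4 non-retinal eye event that settles to Grade 1 or less within 14 days, and neither document resolves the contradiction. It should be corrected because it concerns when an investigator may re-expose a patient after the most severe graded eye toxicity.

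Its size is small. It touches one combination of grade and duration, dosing is interrupted either way, and the sponsor exception could permit a restart even under the stricter row. The conclusion assumes that other eye disorders carries its plain meaning and is not confined to the retina by the row label.

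Two stronger inferences are not supported. The toxicology and phase I findings show why ocular rules matter, but they do not show that Grade 4 eye events are to be expected at the trial dose. Nor does the ambiguity reach the efficacy design: the PFS6 model, sample size and operating characteristics do not depend on it.

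**What to change.** In the next amendment, make two linked edits to the Eye Disorders block of Table 6-3:

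1. Change the trigger of the other ocular/visual toxicity row from Grade 3 and above to Grade 3 only, and keep its present action.
2. Move the discontinue instruction for other Grade 4 eye disorders out from under the retinal label, for example as a Grade 4 line in the other-ocular row. Retinal vein occlusion and Grade 4 CSR stay where they are.

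Each grade of non-retinal event then has one final action. The other-ocular row should stay, although it repeats the Grade 3 action: without it, Grade 3 corneal events would be governed only by an entry filed under a retinal label.

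The cost is a written amendment with ethics committee approval, and health authority approval where required (Protocol Section 12.1). It adds no visits, assessments or patients. It removes any automatic restart after a quickly resolved Grade 4 non-retinal event, but the case-by-case exception in Section 6.2.1 remains available. If the sponsor did intend automatic restart for these events, the amendment should state that instead and confine the discontinue entry to retinal disorders.

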9. ECOG performance status ≤ 2 . Assessment via Karnofsky Performance Status (KPS) and subsequent conversion to ECOG is acceptable (Ma et al, 2010).
10. Able to read and/or understand the details of the study and provide written evidence of informed consents as approved by IRB/EC.
11. Recovery from adverse events of previous systemic anti-cancer therapies to baseline or no more than grade 2, except for the following:
 - a. Alopecia
12. Able to swallow oral medication.
13. Willing and able to comply with scheduled visits, treatment plan and laboratory tests.

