- A third or subsequent reduction (to 50 mg) in dose may be allowed if the patient is clearly benefiting from study treatment (i.e., stable disease, partial response, or complete response) but is experiencing adverse events that prevent continued treatment at the already reduced dose.

Table 6-2 Dose reduction table

Dose level	BGJ398	
Dose level 0	125 mg	Starting dose
Dose level -1	100 mg	
Dose level -2	75 mg	
Dose level -3	50 mg	Allowed only if patients is clearly benefiting from study treatment, but is experiencing AE that prevent continued treatment at dose level -2

Table 6-3 Criteria for interruption and re-initiation of BGJ398 treatment

Worst Toxicity CTCAE using the current active CTCAE version	Recommended Dose Modifications any time during a cycle of therapy
Cardiac disorders	
Cardiac - Prolonged QTcF interval	
Grade 1 and 2 : QTcF ≥ 481msec and ≤ 500 msec (asymptomatic)	
Maintain dose level of BGJ398
 
 ● ECG assessments should be performed for 2 additional cycles at the same frequency as in cycle 1, or as clinically indicated. If ECG assessments show no QTcF ≥ 481 msec, for subsequent cycles ECG monitoring will be performed as per visit schedule. ● If ECG assessments are still abnormal (QTcF ≥ 481 msec and ≤500 msec), then ECG monitoring must continue at the same frequency as in cycle 1 for all subsequent cycles.

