
9.0 mg/dL regardless of duration or dose of phosphate lowering therapy (Sevelamer).
 
(Optimize/maximize dose and schedule of phosphate lowering therapy in accordance with package insert, country or institutional guidelines).
	
Restart BGJ398 at the same dose level with maximal phosphate binder dosing if the patient did not receive maximal phosphate binder dosing for serum phosphorus > 7.0 mg/dL for > 7 days.
 
Reduce one dose level of BGJ398 if the patient had received maximal phosphate lowering therapy for serum phosphorus >7.0 mg/dL for > 7 days or if patient had a one-time serum phosphorus of > 9.0 mg/dL. Restart BGJ398 with maximal phosphate binder dosing.
 
It is recommended that phosphate binder dosing continues during BGJ398 dose interruptions for hyperphosphatemia and that serum phosphorus values be monitored frequently, e.g. every 2-3 days.
 
Phosphate binder dosing should be held during the week off BGJ398 therapy each cycle (Days 22-28) and during BGJ398 dose interruptions for non-hyperphosphatemia adverse events.

Hypercalcemia Serum calcium grade 2
 
Serum calcium ≥ grade 3
	
Hold BGJ398 dose until resolved to grade 1 or baseline:
 
 • if resolved ≤ 7 days after suspending BGJ398, maintain dose level • if resolved > 7 days after suspending BGJ398, ↓ 1 dose level 
Discontinue patient from the study

Nervous system disorders	

Neurotoxicity Grade 2
 
Grade ≥ 3
	
Omit dose of BGJ398 until resolved to CTCAE Grade ≤ 1, then ↓ 1 dose level of BGJ398
 
Discontinue patient from study drug treatment

GI disorders	

Pancreatitis Grade ≥ 2
	
Discontinue patient from study drug treatment

Worst Toxicity CTCAE using the current active CTCAE version	Recommended Dose Modifications any time during a cycle of therapy

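### Table 6-3 ends with unconditional stopping rules for a third dose reduction and for a delay over 14 days, while the Section 6.2.1 text, Table 6-2 and Section 7.1.4.1 between them allow continuation by agreement with the sponsor, and nothing says which prevails.

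*Protocol*

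**What the plan says.** Tables 6-2 and 6-3 are printed inside Section 6.2.1 of the protocol, so the comparison is between the running text of that section and its own tables.

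- **More than two reductions.** The text allows two and adds "Patients must discontinue BGJ398 if toxicities persist following 2 dose reductions", unless continuation is allowed in discussion with the sponsor. Among the situations that may justify continuing it lists: "A third or subsequent reduction (to 50 mg) in dose may be allowed if the patient is clearly benefiting from study treatment". Table 6-2 carries a matching dose level -3 of 50 mg. The closing rule of Table 6-3 reads "Patients who require more than two dose reductions of BGJ398 will be discontinued from study drug treatment".
- **Delay over 14 days.** The text says the patient should be discontinued unless continuation is allowed in discussion with the sponsor, and gives as an example "A dose delay of > 14 days has occurred, but the patient is clearly benefiting from study treatment". Section 7.1.4.1 (premature withdrawal) keeps the same exception. The closing rule of Table 6-3 says "then study treatment must be stopped".
- **General override.** The text also says that, in exceptional situations, treatment may continue although a stopping rule has been met. This is decided case by case after discussion between sponsor and investigator. Table 6-3 neither repeats this clause nor refers to it.
- **Recovery level.** The text resumes treatment at baseline or Grade 1 or lower. Several Table 6-3 rows, including diarrhea, fatigue and other Grade 3 events, require Grade 1 or lower and offer no baseline alternative. Inclusion criterion 11 asks for "Recovery from adverse events of previous systemic anti-cancer therapies to baseline or no more than grade 2".
- **Recurrence.** The text requires discontinuation, unless the sponsor agrees otherwise, in this situation: "If treatment is resumed at the lower doses of study drugs, and the same toxicity recurs with the same or worse severity". Some Table 6-3 rows reduce by one level and do not mention recurrence.

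**The concern.** These passages decide whether a patient stays on drug. Section 6.2.1 and Table 6-3 are meant to be used together, and a site with a patient in one of these situations finds two instructions of different force. Section 12 adds that no authorized deviations are permitted. A site that continues a patient with the sponsor's agreement under the text could therefore still be recorded as having departed from the table.

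Two things are at stake. The first is consistent handling of patients with the same toxicity. The second is the tolerability endpoint in Table 3-1 (interruptions, reductions and dose intensity), which would partly reflect which text was followed rather than how the drug was tolerated.

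**Working it through.** No sample-size or power figure is involved. The check sets the passages side by side and works through cases.

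**Step count (Table 6-2).** 125 → 100 mg is reduction 1, 100 → 75 mg is reduction 2, and 75 → 50 mg is reduction 3. Since 3 > 2, a patient who needs the 50 mg level always meets the closing rule of Table 6-3.

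| Case | Section 6.2.1 text (and Table 6-2, 7.1.4.1) | Table 6-3 |
|---|---|---|
| A. Clear benefit, adverse event prevents continuing at 75 mg | May go to 50 mg after discussion with the sponsor | Discontinued |
| B. Clear benefit, delay over 14 days | May remain on treatment after discussion with the sponsor | Treatment stopped |
| C. Enters with residual Grade 2 fatigue, worsens to Grade 3, returns to Grade 2 | Back at baseline: resume | Grade 1 or lower not reached: still held, and discontinued if not resolved within 7 days |
| D. Other Grade 3 event recurs at Grade 3 on 100 mg | Discontinue unless the sponsor agrees | Hold, then one level down; silent on recurrence |

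A and B are direct conflicts. 

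C is a secondary point. The diarrhea and other-Grade-3 rows work in the same way, except that the hold ends in a stop through the 14-day rule. The mismatch also runs the other way: the asymptomatic amylase/lipase row restarts at Grade 2 or lower, which is looser than the text.

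D is an ambiguity. The QTcF and Grade 3 diarrhea rows state their own recurrence rule (discontinue), and the amylase/lipase row says to hold and discuss. Because some rows address recurrence, silence in others, such as hyperphosphatemia and other Grade 3 events, could mean that the general rule applies or that a further reduction is intended.

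**Effect on a reported quantity, case A.** SAP Section 2.4.1 defines relative dose intensity as actual over planned dose intensity. Both share the same duration, so the ratio is actual over planned cumulative dose, with planned dose counted up to the last administration. Assume, for illustration, one full 21-day dosing period at each level, no interruptions, and 125 mg as the planned dose throughout. The 21 days cancel.

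- Stopped after 75 mg: (125 + 100 + 75) / (3 × 125) = 300 / 375 = 0.80, with two reductions.
- Continued for one cycle at 50 mg: (125 + 100 + 75 + 50) / (4 × 125) = 350 / 500 = 0.70, with three reductions.

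The same patient moves from the 0.75 to below 0.9 category of protocol Section 10.5.3.5 to the 0.5 to below 0.75 category, and is or is not counted as discontinued at that point.

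**The case against.** The strongest reply is the general override. It speaks of stopping rules without limit, and the two examples after it are exactly the delay and the third reduction. Read this way, Table 6-3 gives the default and the text gives the exception, so only a cross-reference is missing. Much of this stands. The default in every passage is to stop, and continuing requires discussion with the sponsor. A reader might infer that sites can stop or continue patients as they choose; the documents do not support that. The override does not remove the conflict, because the closing rules are worded as absolute, do not point to it, and no text ranks the two.

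Other stronger readings also fail:

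- **Grade 2 neurotoxicity at entry.** The row reads "Omit dose of BGJ398 until resolved to CTCAE Grade ≤ 1, then ↓ 1 dose level of BGJ398", so it might seem that a patient with stable Grade 2 neurotoxicity is on hold from the first dose. Section 8.1.1 defines an adverse event as something new or worsened after consent, so a stable prior condition does not trigger the row. Worsening to Grade 3 discontinues the patient in any case.
- **75 mg reachable only through a different toxicity.** The recurrence rule covers the same or worse severity only and allows sponsor agreement. A milder recurrence or an agreed continuation can also lead there.
- **Several of the 34 patients affected.** The 4 of 25 (16%) in Section 1.2.1.2.1 counts any cycle 1 interruption or reduction. It does not measure third reductions, delays over 14 days or recurrence.
- **PFS6 distorted.** Under Section 7.1.5, patients who stop for reasons other than progression still have MRI every 8 weeks until progression, new anticancer therapy or death. Stopping changes exposure but does not by itself end ascertainment.
- **Loss from the Per-Protocol Set.** SAP Section 2.2 requires no protocol deviations, but the exclusions listed in its Table 2-3 concern inclusion criteria and prohibited medication. Exclusion over a dosing-rule conflict is possible but not established.

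**Conclusion.** The point holds as an internal inconsistency in current text. On a third reduction and on a delay over 14 days, Table 6-3 mandates a stop where the other passages allow the sponsor to agree otherwise. Read literally, it makes a listed dose level unreachable. The recovery level is a real but narrower mismatch, confined to patients who enter with a residual Grade 2 event and worsen on study, and to the amylase/lipase row. Recurrence at a reduced dose is an unanswered question rather than a proven contradiction, since silence in a row may simply leave the general rule in force.

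No frequency can be derived from the documents. The size can be stated only per patient: a stop or a continuation, two or three reductions, and in the illustration above a relative dose intensity of 0.80 or 0.70. Any effect on PFS6 runs through exposure and is indirect. The passages should be reconciled; this review takes no position on which clinical rule is right.

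**What to change.** Reconcile the text of Section 6.2.1, Table 6-2, Section 7.1.4.1 and the rows and closing rules of Table 6-3 into one governing statement that covers:

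1. more than two dose reductions, including whether the 50 mg level is available;
2. a delay over 14 days;
3. recurrence of the same toxicity at a reduced dose, and whether the general rule applies to rows that do not mention it;
4. the recovery level for restarting, including for patients who entered with a Grade 2 event.

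State which text prevails where the table and the section differ, and, if the general override is kept, refer to it in the closing rules of Table 6-3. The same edit should resolve Grade 4 asymptomatic amylase/lipase elevation, for which Table 6-3 gives two instructions (hold and discuss; discontinue). The content of each rule is for the sponsor's clinical team.

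The cost is protocol wording only, with no new data, visits or procedures.
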